4.2.2. Exploratory Endpoints

There are no exploratory endpoints.

5. STUDY OVERVIEW

5.1. Study Design and Description of the Study Device

This is a multicenter, open-label, treatment-only study conducted in the United States. A total of 20 participants is planned for the study. The study will test two treatment parameters. The first 10 participants will be treated at a generator setting of 600 Volts/13 bursts/350 KHz (600V) and the second group of 10 participants at 750 Volts/8 bursts/350KHz (750V). In the 600V group, the first 5 participants will be enrolled/treated with the investigational device sequentially with at least 14 days observation time between each procedure. In the 750V group, the first participants will be enrolled/treated with the investigational device sequentially with at least 6 days observation time between each procedure.

Participants with T2D inadequately controlled on 2-3 non-insulin glucose-lowering medication(s) will be screened for study eligibility. Eligible participants who consent to participate in the study will maintain his/her background glucose-lowering medication(s) stable (no medication or dose change) for at least 12 weeks prior to baseline visit.

The index procedure will be performed under general anesthesia or deep sedation and within 21 days from the baseline visit. Participants will undergo endoscopic screening immediately prior to the DMR procedure, and eligible participants will undergo the DMR procedure. Participants may be discharged per local hospital's guideline; an overnight stay is not required but allowed per local policy and investigator's clinical judgement. A participant is enrolled in the study when the Endogenex catheter insertion is attempted. Participants excluded during endoscopic screening will be considered a screen failure and will be followed for four weeks after the procedure for safety.

Post index procedure, participants will be on a transitional diet consisting of clear liquids for 24 hours followed by a full liquid diet for 3 days, pureed food for 3 days, and soft food for one week, and then return to normal food as tolerated.

Background medication will be titrated to the pre-procedure dose and maintained for 24 weeks post index procedure and the transitional diet period per Section 6.2. After the 24-week follow-up visit, participants will be managed according to the current (2021) guidelines of the American Diabetes Association² and their glucose-lowering medications will be optimized to achieve individualized A1c goals, which for most individuals is a target of less than 7.0%.

Participants will receive lifestyle-modification counseling sessions at scheduled intervals to promote adherence to a diet and lifestyle suitable for individuals with diabetes. Counseling will be provided by a member of the research team (endocrinologist, dietitian, nurse, etc.) trained in the delivery of lifestyle counseling for diabetes.

Participants will be followed up for 48 weeks after the index procedure. The primary endpoint will be evaluated at 12 weeks post procedure.

5.2. Schedule of Assessments

Reference Appendix 2. Schedule of Activities in the study protocol for the complete schedule of assessments.

5.3. Sample Size Justification

The study plans to enroll 20 participants and test two treatment parameters (600 volts and 750 volts), with 10 participants treated in each group. As this study is intended to characterize device safety and feasibility outcomes, formal sample size and power calculations based on hypothesis testing against a priori statistical objectives are not relevant; a sample size of 10 in each group and 20 in total is considered to be sufficient for the objectives of this investigation.

5.4. Estimated Duration of Patient Participation

Total duration on study will be calculated as the difference between the date of informed consent and the last on-study observation. All calculations defining the duration on study will be performed relative to the date of informed consent and follow the algorithm DURATION = ([STUDY COMPLETION OR WITHDRAW DATE – INFORMED CONSENT DATE])+1.

The first participant enrolled was in Q4, 2021; the estimated enrollment duration is 18 months.

6. ANALYSIS POPULATIONS

Patients will be considered enrolled in the study once the patient has passed endoscopic screening. Screen failures are defined as patient who consented to participate in the clinical study and started the screening tests specified by the protocol but are not subsequently enrolled in the study.

The primary and secondary safety analyses will be performed using the ITT. The primary effectiveness analyses will be performed using the FAS population. The Per-Protocol population and Completed-Cases population will be used for the sensitivity analyses of the primary and secondary effectiveness endpoints.

Intent-to-Treat: The Intent-to-Treat population includes all enrolled patients, regardless of the patient having received the target treatment (at least 6cm of duodenum treated). The point of enrollment occurs when a patient has provided written informed consent and an energy delivery has been attempted during the index procedure.

Full Analysis Set: The FAS population consists of the ITT population patients who received the target treatment (at least 6 cm of duodenum treatment) and that have at least one post-treatment follow-up examination.

Per-Protocol: The Per-Protocol population is a subset of the FAS population and includes all patients who received the target treatment, do not have any major eligibility violations, and maintained stable glucose-lowering medications for 24 weeks post-procedure. The definition of what constitutes a major eligibility violations will be established before the study database is locked.

Completed Cases: The Completed Cases population is a subset of the Per-Protocol population and includes all patients who received the target treatment, do not have any major eligibility violations, and maintained stable glucose-lowering medications for 24 weeks post-procedure, and completed the final Week 48 End of Study Visit.

7. GENERAL CONSIDERATIONS

Post-text Tables and Listings will be prepared in accordance with the current ICH Guidelines. The header of each Table and Listing will include the sponsor's name and the study number. The information and explanatory notes to be provided in the "footer" or bottom of each Table and Listing will include the following information:

1. Date and time of output generation.
2. SAS® program name, including the path that generates the output.
3. Any other output specific details that require further elaboration.

In general, tables will be formatted with a column displaying findings for all patients combined. Row entries in tables are made only if data exist for at least one (1) patient (*i.e.*, a row with all zeros will not appear). The only exception to this rule applies to tables that list the termination status of patients (*e.g.*, reasons for not completing the study). In this case, zeros will appear for study termination reasons that no patient satisfied. The summary tables clearly indicate the number of patients to which the data apply, and unknown or not performed are distinguished from missing data. Tables, Listings, and Figures will provide the units of measurement, unless there are no units. Results recorded at single times during the study will be presented using the *Level 1* displays for the ITT Population; the example structure is presented below.

Level 1a Display

Parameter and Statistic	Device Generation 1 / 600 Volts / Single Treatment	Device Generation 1 / 600 Volts / Double Treatment	Device Generation 2 / 750 Volts / Double Treatment	All Patients
Age				
Sex				

Level 1b Display

Parameter and Statistic	Device Generation 1 / 600 Volts / Single Treatment	Device Generation 1 / 600 Volts / Double Treatment and Device Generation 2 / 750 Volts / Double Treatment	All Patients
Age			
Sex			

The *Level 2* displays will be used for summarizing the incidence of AEs. An example of the layout for AEs by severity is presented below.

Level 2a Display

System Organ Class Preferred Term	Device Generation 1 / 600 Volts / Single Treatment	Device Generation 1 / 600 Volts / Double Treatment	Device Generation 2 / 750 Volts / Double Treatment	All Patients
SOC PT				

Level 2b Display

System Organ Class Preferred Term	Device Generation 1 / 600 Volts / Single Treatment	Device Generation 1 / 600 Volts / Double Treatment and Device Generation 2 / 750 Volts / Double Treatment	All Patients
SOC PT			

The *Level 3* display will be used for summarizing the parameters recorded multiple times during the follow-up visits. An example of the layout is presented below; rows will be repeated for all visits where a measurement is recorded using the expanded time windows.

Level 3a Display

Parameter and Statistic	Observation Time	Device Generation 1 / 600 Volts / Single Treatment	Device Generation 1 / 600 Volts / Double Treatment	Device Generation 2 / 750 Volts / Double Treatment	All Patients
HbA1c	Baseline				
HbA1c	Post-Procedure Visit xxx				
HbA1c	Change from Baseline				

Level 3b Display

Parameter and Statistic	Observation Time	Device Generation 1 / 600 Volts / Single Treatment	Device Generation 1 / 600 Volts / Double Treatment and Device Generation 2 / 750 Volts / Double Treatment	All Patients
HbA1c	Baseline			
HbA1c	Post-Procedure Visit xxx			
HbA1c	Change from Baseline			

There will be 2 sets of comparative analyses prepared, each predicated on different combinations of device generation, voltage, and single vs. double treatment. The planned comparisons are outlined below.

Comparison Set 1

Device Generation 1 / 600 Volts / Single Treatment vs.

Device Generation 1 / 600 Volts / Double Treatment vs.

Device Generation 2 / 750 Volts / Double Treatment

Comparison Set 2

Device Generation 1 / 600 Volts / Single Treatment vs.

Device Generation 1 / 600 Volts / Double Treatment plus Device Generation 2 / 750 Volts / Double Treatment

Supportive individual patient data Listings will be sorted and presented by site number, patient number and visit date, if applicable. Listings will also include the number of days relative to the DMR index procedure. Specific algorithms are discussed for imputing missing or partially missing data, if deemed appropriate, under specific data topics. Imputed or derived data will be flagged in the individual patient data Listings. Imputed data, restricted to dates, will not be incorporated into any raw or primary datasets from the electronic capture system. The imputed data will be retained in the derived / analysis datasets.

Summary statistics will consist of the number and percentage of responses or counts at each level for categorical variables (e.g. race). For continuous variables, and the sample size (n), mean, median, standard deviation (SD), minimum, and maximum values will be presented.

All mean and median values will be formatted to one more decimal place than the measured value. Standard deviation values will be formatted to two more decimal places than the measured value. Minimum and maximum values will be presented with the same number of decimal places as the measured value.

The number and percentage of responses will be presented in the form XX (XX.X%).

- All summary tables will include the analysis population sample size (i.e., number of patients).
- Relative Study Day 1 is defined as the day the patient underwent the DMR study procedure. All study days are determined relative to the day the patient underwent the DMR study procedure.
- Baseline values will be defined as those values recorded immediately prior to the DMR study procedure.
- Change from baseline for ratio data will be calculated as follows:
$$\text{Change} = \text{Post-Procedure value} / \text{baseline value}.$$
- Change from baseline for differences will be calculated as follows:
$$\text{Change} = \text{Post- Procedure value} - \text{baseline value}.$$
- Missing data may have an impact upon the interpretation of the trial data. However, given the feasibility nature of this study, coupled with the number of patients within a Comparison Set, multiple imputation will not be attempted. The primary presentation of the results will be based on the observed data. A methodology is defined in this section for addressing missing dates.
- Date variables will be formatted as DDMMYY for presentation; SAS Date9. format.
- Months will be converted to days by dividing by 30.42 and rounding up to achieve an integer value.
- SAS® Version 9.4 will be the statistical software package used for all data analyses.
- All data from this study will be presented in a listing.
- Table and listing numbering will follow ICH guidelines for post-text table and listing numbering.

For Adverse Event reporting, which includes primary and secondary variables, the primary analysis will be based on Patient counts (e.g., the number and percentage of Patients with events among the total number of Patients). The data will be presented in the format of p% (x/N) [e], with p and x being the percentage and number of Patients with events, respectively, N being the sample size of the analysis population, and e being the total number of events occurred in the x Patients. Asymptotic confidence limits will be presented based on the normal approximation to the binomial distribution for differences in proportions. Exact confidence intervals will be used for all other presentations.

7.1. Multiple Comparison/Multiplicity

This is a feasibility study and the hypothesis testing that is being performed is strictly for informative purposes. There will not be any adjustment for multiplicity.

7.2. Adjustments for Covariates and Stratification Factors

Data will be presented by individual subgroups if there are a sufficient number of patients to warrant the breakdown. There are no planned stratification factors to be included in the models of the 5 different Comparison Sets.

7.3. Handling of Missing Data

7.3.1. Missing and Censored Data

All tabulations and analyses will be based on the observed data without imputation, with the exception of dates.

7.3.2. Subgroup Analyses: Assessing the Effect of Pre-Specified Factors on a Continuous Parameter

Based on the limited enrollment and sample size from the clinical investigation, the proposed tabulations for the individual subgroups may not be possible. Subgroup analyses will follow the follow approach where possible and if it is clinically indicated to address a specific research question.

The breakdown of safety and effectiveness will follow the FDA Guidance entitled *Evaluation and Reporting of Age-, Race-, and Ethnicity-Specific Data in Medical Device Clinical Studies* (Document issued on September 12, 2017). Specifically, the guidance provided in Section VI. entitled *Recommendations for Submitting Age-, Race-, and Ethnicity-Specific Data in Submissions to the Agency and Reporting in Public Documents*, Part A: Enrollment Demographics, Baseline Characteristics & Co-Morbidities.

Subgroup analyses by the following baseline characteristics will be provided if there are a sufficient number of patients that warrant this breakdown:

- age group (<65, \geq 65 years)
- race
- sex
- ethnicity
- duration of diabetes (<median, \geq median)
- duration of diabetes (\leq 5, >5 to \leq 10, >10 years)
- HbA1c (\leq 8.5%, >8.5%)
- renal impairment (eGFR <60, \geq 60 mL/min/1.73m²), and
- BMI group (<30, \geq 30 to <35, \geq 35 kg/m²).

7.3.3. Safety Measures

Descriptive summaries for all safety measures will be based on observed data. No imputation of missing scores or observations will be implemented for safety outcomes.

7.3.4. Dates for Medical Events

The completely or partially missing onset and resolution dates of medical events including AEs will be imputed in a conservative fashion as follows:

Date	Type of Missing Date	Handling of Missing Date
Event onset date (e.g., YYYY-MM-DD)	Completely missing	No imputation will be applied.
	Only YYYY is available	Use the first day of YYYY to impute the missing month and date parts of the onset date
	YYYY and MM are available but DD is missing	Use the first day of MM to impute the missing date part of the onset date
Event resolution date (e.g., YYYY-MM-DD)	Completely missing	No imputation will be applied. The event will be considered ongoing (i.e., not resolved) at the Study Exit date.

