10.1.2. Handling of Missing or Partial Adverse Event Dates

Handling of Missing AE Start-dates (missing AE stop-dates are not filled)

Rules for assuming a full date for AEs with incomplete or missing start-dates are addressed below. In the unusual case that the month portion of an AE start-date is missing but the day portion is not missing, the day portion of the AE will be assumed to be missing. Likewise in the case where the year portion of an AE start-date is missing but the month and/or day portion is not missing, the month and/or day portion of the AE will be assumed to be missing. All missing portion(s) of the AE start-dates will be handled using the same rules.

- In the event that the day portion (and only the day portion) of the AE onset date is missing:
 - If the AE started in the same month and year as the study procedure, the AE onset date will be assumed to be the date of the study procedure (*i.e.*, Study Day 1);
 - Otherwise, the AE onset date will be assumed to be the 15th day of the given month and year, *e.g.*, XX-DEC-2005 → 15-DEC-2005 where XX represents an unknown value.
- In the event that the day and month portion (and only the day and month portion) of the AE onset date are missing:
 - If the AE started in the same year as the study procedure, the AE onset date will be assumed the study procedure (*i.e.*, Study Day 1);
 - Otherwise, the AE onset date will be treated as June 15th of the given year, *e.g.*, XX-XXX-2005 → 15-JUN-2005.

- In the event that the day, month, and year portion of the AE onset date are missing, the start-date of the AE will be assumed to be the study procedure (*i.e.*, Study Day 1).

Special Cases on Missing AE Start-dates

- If the assumed AE onset date using the above rules for handling of missing AE dates
 - is earlier than the screening date, the assumed AE onset date will be reset and assumed to be the screening date.
 - is later than the reported AE stop-date, the assumed AE onset date will be reset and assumed to be the AE stop-date.
 - is later than the database lock date and AE stop-date missing, the AE will be assumed to be a follow-up AE and not treatment-emergent.

Several Examples of Handling Missing AE Start-dates

Assume that the study procedure for a patient is 04-FEB-2005 and the Screening Date is 18-JUL-2004

- Example: The day portion (and only the day portion) of the AE onset date is missing:
 - If the AE onset date is XX-DEC-2004 then the assumed AE onset date is 15-DEC-2004.

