 - If the AE onset date is XX-FEB-2005 then the assumed AE onset date is 04-FEB-2005, as the AE started in the same month and year as the study procedure.
- Example: The day and month portion (and only the day and month portion) of the AE onset date are missing
 - If the AE onset date is XX-XXX-2004:
 - then the assumed AE onset date is 15-JUN-2004 using the rules;
 - but this is a special case since the assumed date 15-JUN-2004 is before the patient's screening date 18-JUL-2004. Therefore, the assumed AE onset date will be reset and assumed to be 18-JUL-2004.
 - If the AE onset date is XX-XXX-2005 then the assumed AE onset date is 04-FEB-2005, as the AE started in the same year as the study procedure.
- Example: The day, month, and year portion of the AE onset date are missing (*i.e.*, if the AE onset date is XX-XXX-XXXX), then the assumed AE onset date is 04-FEB-2005).

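### SAP 7.3.4 and SAP 10.1.2 assign different onset dates to every kind of incompletely dated adverse event, and the SAP does not say which governs; 7.3.4 can date a procedure-month event before the procedure (minor).

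*SAP*

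**What the plan says.** SAP 7.3.4 (Dates for Medical Events) names adverse events within its scope and says that their incomplete dates "will be imputed in a conservative fashion as follows". For onset:

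- Day missing: "Use the first day of MM to impute the missing date part of the onset date".
- Only the year known: "Use the first day of YYYY to impute the missing month and date parts of the onset date".
- Wholly missing: left missing.

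SAP 10.1.2 (Handling of Missing or Partial Adverse Event Dates) covers the same onset dates:

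- Day missing: the procedure date if the event began in the procedure month; otherwise "the AE onset date will be assumed to be the 15th day of the given month and year".
- Day and month missing: the procedure date if in the procedure year; otherwise 15 June.
- Wholly missing: "the start-date of the AE will be assumed to be the study procedure".

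SAP 10.1.2 also moves an assumed onset forward to the screening date if it would be earlier, and back to the reported stop date if it would be later. SAP 7.3.4 has no such bounds.

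Two sentences in SAP 7 (General Considerations) bear on precedence, and they point different ways. One is "Specific algorithms are discussed for imputing missing or partially missing data, if deemed appropriate, under specific data topics". The other is "A methodology is defined in this section for addressing missing dates". Neither 7.3.4 nor 10.1.2 refers to the other.

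SAP 9 counts related serious events for the primary endpoint from the start of the procedure to relative study day 84. SAP 7 makes the procedure day Day 1.

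**The concern.** Two programmers could each follow the SAP and date the same event differently. The choice matters at the start of the primary window. A first-of-month rule with no floor at the procedure date places an early post-procedure event before the procedure, where it no longer counts. The days just after the procedure are when a related event would be expected. A wholly undated event gets no date under 7.3.4, so it cannot be placed in the window, while 10.1.2 counts it on Day 1.

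The SAP's tables of post-procedural events by relationship (14.3.4 to 14.3.5.1a) are exposed in the same way. Protocol 11.4.2 treats pre-procedure events as medical history. The supplied protocol is No. 196 and the SAP cites Doc. No. 346, so that last consequence is secondary; the conflict itself lies wholly within the SAP.

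If the rule is not settled before lock, someone will choose it with the events in view.

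**Working it through.** **1. The SAP's own examples.** SAP 10.1.2 uses a patient with procedure 04-FEB-2005 and screening 18-JUL-2004. Its first result in the procedure month is: "If the AE onset date is XX-FEB-2005 then the assumed AE onset date is 04-FEB-2005". Coding the 10.1.2 rules reproduces all five of its outcomes. The same inputs under 7.3.4 give:

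| Recorded onset | 10.1.2 | 7.3.4 |
|---|---|---|
| XX-DEC-2004 | 15-DEC-2004 | 01-DEC-2004 |
| XX-FEB-2005 | 04-FEB-2005 (Day 1) | 01-FEB-2005 (3 days before procedure) |
| XX-XXX-2004 | 18-JUL-2004 | 01-JAN-2004 (before screening) |
| XX-XXX-2005 | 04-FEB-2005 (Day 1) | 01-JAN-2005 (34 days before procedure) |
| wholly missing | 04-FEB-2005 (Day 1) | no date |

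The rules disagree in 5 of 5.

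**2. How often 7.3.4 predates the procedure.** Over 365 possible procedure dates, a day-missing event in the procedure month is dated before the procedure for all but the 12 firsts of the month: (365 − 12)/365 = 353/365 = 96.7%.

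**3. Effect on the primary window, day missing.** Assumptions, not from the documents: every procedure date in a 365-day year is equally likely, and true onset is equally likely on each study day in the stated range. Window = Days 1-84. I crossed all procedure dates with all onset days, applied each rule, and counted onsets put on the wrong side.

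- Days 1-84: 365 × 84 = 30,660 combinations. SAP 7.3.4 loses 5,373/30,660 = 17.5%. All of these are in the procedure month, where it loses 5,373/5,738 = 93.6%.
- Days 1-7: 7.3.4 loses 2,219/2,555 = 86.8%; 10.1.2 loses 0.
- Days 1-28: 7.3.4 loses 5,348/10,220 = 52.3%; 10.1.2 loses 0.
- Days 85-337: 365 × 253 = 92,345 combinations. Wrongly brought in: 7.3.4 5,373 (5.8%); 10.1.2 1,523 (1.6%).

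The loss under 10.1.2 on Days 1-84 depends on its stop-date reset, which pulls back an assumed 15th that falls after the event ended:

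| Stop date | Lost under 10.1.2, Days 1-84 |
|---|---|
| same day as onset | 0 (0%) |
| 3 days after onset | 468/30,660 = 1.5% |
| 7 days after onset | 924/30,660 = 3.0% |
| 14 days or more after onset, or missing | 1,260/30,660 = 4.1% |

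The reset cannot change the 1,523 brought in: their true onset, and so their stop date, is already later than the assumed date.

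Total misplaced over Days 1-337 (365 × 337 = 123,005):

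- 7.3.4: (5,373 + 5,373)/123,005 = 8.7%.
- 10.1.2: from (0 + 1,523)/123,005 = 1.2% to (1,260 + 1,523)/123,005 = 2.3%.

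**4. What one event does.** The SAP plans 20 patients. Exact (Clopper-Pearson) 95% intervals: 0/20 = 0%, upper limit 1 − 0.025^(1/20) = 16.8%; 1/20 = 5.0%, interval 0.1% to 24.9%.

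**The case against.** The best reply is that precedence is clear in practice. SAP 10.1.2 is headed for adverse event dates, sets out special cases and works through examples, and SAP 7 points to algorithms under specific topics. On an ordinary specific-over-general reading a programmer would use it, and the harm needs the generic table to be chosen instead. This carries weight and is why 10.1.2 should be kept. It does not close the gap: SAP 7 also says the missing-date method is in that section, and 7.3.4 names adverse events. SAP 7.3.3, which rules out imputing missing scores or observations for safety outcomes, does not settle it either, since 7.3.1 exempts dates.

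Second, the protocol requires an onset date on the adverse event form, prompt reporting of serious events, automated data checks and source verification. An undated serious event should be rare. This stands and limits the practical reach.

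Third, an earliest-possible onset can fairly be called conservative for event duration, and the SAP does not define the word. That also stands. The rule is unfavourable to safety counting only at the procedure-date boundary.

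A reader might infer that 17.5% of related serious events would be lost. The documents do not support that: the figure applies only to events with a missing day, and no frequency for that is given. A reader might also take 4.1% as a fixed error of 10.1.2; it is an upper bound, because of the stop-date reset.

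**Conclusion.** The conflict is real and covers every type of incomplete adverse event onset. Precedence can be inferred in favour of 10.1.2 but is not stated. If 7.3.4 were followed, nearly every day-missing event in the procedure month would be dated before the procedure and dropped from the primary count.

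The comparison favours 10.1.2 throughout the range examined, and most strongly in the first four weeks. The percentages rest on a missing day and on uniform procedure and onset dates; only the day-missing case was quantified by window. The expected effect on the primary result cannot be derived from the documents, because they do not say how often onset dates are incomplete. The documents do not show that 7.3.4 would be the rule applied, or that any result would be wrong. Severity: minor.

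**What to change.** Before database lock, remove adverse events from the scope of SAP 7.3.4 and state that SAP 10.1.2 alone governs their onset dates. No new imputation rule is needed.

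Optional additions are to query any serious event with an incomplete onset date, and to note in the report any related serious event whose place in the primary window depends on imputation. Imputed dates are already to be flagged in the listings, so such events can be found.

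The cost is one sentence in the SAP. The downside is that 10.1.2 counts wholly undated events as Day 1 and keeps the small residual misplacement shown above.
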